### 4 Statistical Analysis

#### 4.1 The coincidence rate of the panel and the comparison method

For each gene locus, a four-grid table was used to calculate the positive coincidence rate, negative coincidence rate, positive predictive value, negative predictive value, total coincidence rate and 95% confidence interval of the assessment reagent and the comparison method. Using statistical software, Kappa test is used to determine whether the two detection methods are statistically significant.

Table 2. Results statistics

Genetron Lung Cancer	Comparison method		Total
Panel	Positive	Negative	
Positive	A	В	A+B
Negative	C	D	C+D
Total	A+C	B+D	A+B+C+D

A sample with a mutation genotype is judged as positive, and a sample with no mutation genotype is judged as negative

The calculation formula is:

Positive coincidence rate=A/(A+C)×100%

Negative coincidence rate =  $D/(B+D) \times 100\%$ 

Positive predictive value (PPV)=A/(A+B)×100%

Negative predictive value (NPV)=D/(C+D)×100%

Total coincidence rate=(A+D)/(A+B+C+D)×100%

95% confidence interval calculation formula:  $p\pm1.96\times[p(1-p)/n]^{1/2}$  (where p is the positive coincidence rate, negative coincidence rate, positive predictive value, negative predictive value, total coincidence rate, n is the sample size, if p>0.9, use Wilson score method for correction).

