#### 3.2 Clinical Trial Sample Screening

#### 3.2.1 Sample Type and Size

The samples in this study are confirmed tissue biopsy samples, which are retrospective samples.

The total number of samples in this clinical trials is 1052. It is planned to be carried out in at least 4 clinical trial institutions, and 3 of them will enroll no less than 255 samples. In case of objective reasons, when the sample size is insufficient, the centers can make appropriate adjustments or increase clinical trial institutions under the premise of ensuring the total amount. It is planned that the ratio of positive samples shall not be less than 30%, and the rare mutation types shall be counted according to the clinical occurrence, which should be statistically significant. Gene locus below the above standards can no longer be included in clinical data statistics.

The analysis of the selected number of case samples is statistically significant, and the conclusions obtained are reasonable and effective, which can make a scientific evaluation of the Genetron Lung Cancer Panel and save social costs to the greatest extent. If all types of specimens are not received as planned due to other reasons, the final type and quantity of specimens shall be subject to the actual collected specimens after negotiation and agreement between the two parties.

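### Section 4.1 defines n only as the sample size for all five confidence intervals; taken as written, the positive-agreement interval is too narrow, about 1.8-fold at 30% positives

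*Combined protocol and SAP*

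**What the plan says.** Section 4.1 builds one two-by-two table per gene locus and prints a formula for each rate. Two examples are "Positive coincidence rate=A/(A+C)×100" and "Positive predictive value (PPV)=A/(A+B)×100". The remaining denominators are B+D for negative agreement, C+D for NPV and A+B+C+D for total agreement.

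A single interval follows for all five rates, p ± 1.96×[p(1−p)/n]^½. The note on its symbols lists the five rates as p and ends "total coincidence rate, n is the sample size", which is the only definition of n. For high rates the method changes ("if p>0.9, use Wilson score method for correction"), but n is not redefined.

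Section 3.2.1 gives the size of the study: "The total number of samples in this clinical trials is 1052". It plans at least 30% positive samples without saying whether that applies overall or to each locus, and it sets no number of positives for any locus.

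**The concern.** The standard error of a proportion depends on the number of samples in its own denominator. Positive agreement is estimated from the A+C comparator-positive samples only. Entering the whole table as n credits the estimate with information from comparator-negative samples, which say nothing about it. The same slip affects negative agreement, PPV and NPV. It is separate from the choice between Wald and Wilson, since either interval is wrong if n is wrong.

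Positive agreement bears directly on the companion-diagnostic aim in Section 2 (EGFR exon 19 deletion, L858R and T790M; ALK and ROS1 fusions). It is also the rate most exposed, because positives are normally the smaller group. An interval that is too short would overstate how well the panel's detection of these alterations has been established.

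**Working it through.** The plan prints a formula but no numerical interval, expected agreement or count of positives by locus. There is no figure of its own to reproduce, so the check compares the formula under two readings of n.

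**Inputs from the documents.** z = 1.96; Wald for p ≤ 0.9 and Wilson for p > 0.9; the five denominators (all Section 4.1). Total 1052 and at least 30% positives (Section 3.2.1): 0.30 × 1052 = 315.6, taken as 316.

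**Assumed.** The share of positives at a locus (5% to 50% shown) and the true or observed agreement (90% or 95%, with 100% as a special case). The table total is taken as 1052.

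**1. Width ratio for positive agreement.** Under Wald, p cancels:

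ratio = sqrt[p(1−p)/(A+C)] ÷ sqrt[p(1−p)/N] = sqrt(N/(A+C))

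| Positives, of 1052 | Wald ratio | Half-width at p = 0.90, n = A+C | Wilson width ratio at p = 0.95 |
|---|---|---|---|
| 526 (50%) | 1.41 | 2.56 points | 1.42 |
| 316 (30%) | 1.82 | 3.31 points | 1.85 |
| 105 (10%) | 3.17 | 5.74 points | 3.32 |
| 53 (5%) | 4.46 | 8.08 points | 4.85 |

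With n = 1052 the half-width at p = 0.90 is 1.96 × sqrt(0.9 × 0.1/1052) = 1.81 points, whatever the number of positives.

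**2. Where the factor reaches 3.** sqrt(N/(A+C)) = 3 gives A+C = N/9 = 1052/9 ≈ 117, or about 11% of samples.

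**3. Wilson intervals at an observed 95%.** With n = 1052: 93.5% to 96.2%. With n = 316: 92.0% to 96.9%. With n = 53: 85.5% to 98.4%. The square-root rule is exact for Wald and close for Wilson, except at an observed 100%, where the Wilson ratio is larger. With 316 positives the interval is then 99.6% to 100% as written and 98.8% to 100% with n = 316, a ratio of 3.3.

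**4. Coverage.** Apply the Section 4.1 rule to every possible count x of agreeing samples out of A+C, and sum the binomial probabilities of those x whose interval contains the true value. At a true agreement of 95%:

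- 316 positives: about 70% with n = 1052; about 95% with n = 316.
- 526 positives: about 84% with n = 1052.

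A normal approximation agrees: the interval spans ±1.96 × sqrt(316/1052) = ±1.07 true standard errors, which covers about 72%.

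**5. Negative agreement.** The ratio is sqrt(N/(B+D)). At 30% positives, B+D = 1052 − 316 = 736 and the ratio is sqrt(1052/736) = 1.20. At 5% positives it is 1.03.

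**The case against.** The strongest reply is that the wording is loose rather than wrong. The term is not used consistently: the background uses it for the amount of material that testing needs, and the running text of Section 3.2.1 sets it beside the total as something different. Section 4.2 writes the table total as capital N, whereas Section 4.1 uses lower-case n in the ordinary one-proportion formula, with the correct denominators printed just above. Wilson is named without a formula, and standard software given the counts would use the right denominator. All of this stands as a reason to doubt that wrong intervals would actually be reported. It does not repair the definition: Section 4.1 prescribes an explicit formula, and Section 5 requires the protocol to be followed strictly.

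A second reply is that n need not be 1052 even when read literally, because tables are built by locus. The ROS1 fluorescence PCR comparison plans at least 200 samples. With a table total of 200 and an assumed 20 positives, the factor is sqrt(200/20) = 3.2, against sqrt(1052/20) = 7.3 with 1052. This also stands, and it is why the factor is expressed in terms of the table total.

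A reader might infer that the intervals are several times too narrow throughout, or that the trial would claim near-certain sensitivity from 20 to 40 positives. The documents do not support either. No interval is stated, no such counts appear, and at 30% to 50% positives the factor is 1.8 to 1.4. Coverage at such small counts is also a poor guide, because it jumps with the discreteness of the data: at a true 95% it is about 38% with 20 positives, 0% with 30 and 28% with 40.

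**Conclusion.** The point holds as a faulty definition with a calculable effect. One n, described only as the sample size, serves five rates, and it fits one of them. Followed literally, it makes the positive-agreement interval too narrow by about sqrt(table total/(A+C)): 1.4-fold at 50% positives, 1.8-fold at 30%, and (by the Wald formula) more than 3-fold only at about 11% positives or fewer. The result of about 70% coverage assumes a table of 1052, 316 positives at the locus and a true agreement of 95%. Section 3.2.1 does not say that 30% applies to each locus, so factors for rarer loci remain conditional on counts that are not given.

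The effect on negative agreement is small. Point estimates are unaffected, and so is the only numerical agreement criterion, kappa above 0.75 in Section 4.2, which does not use this n. Because no acceptance limit is attached to any of these intervals, a reader should not infer that the trial's conclusion depends on the error. It should be corrected before analysis, but it ranks below the most serious class of problem.

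**What to change.** In Section 4.1, replace the definition of n with: *n is the denominator of the rate concerned: A+C (positive coincidence), B+D (negative coincidence), A+B (PPV), C+D (NPV), A+B+C+D (total coincidence).* State that the Wilson interval uses the same n.

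This is a one-sentence change that needs no new samples or tests. Its only cost is that the reported intervals become wider than those the literal formula would give, most visibly for positive agreement at the rarer loci.

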#### 4.2 Kappa test

The Kappa test method was used to analyze the equivalence of clinical research reagents and comparison methods. Using statistical software, Kappa test was performed on the detection results of clinical research reagents and gold standard, and the k value was calculated. When k>0.75, clinical research reagents and comparison methods have good consistency.

$$Kappa = \frac{P_a - P_c}{1 - P_c}$$
, Where  $P_{a=} = \frac{A + D}{N}$ ,  $P_C = \frac{(A + B)(A + C)}{N} + \frac{(B + D)(C + D)}{N}$ 

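### Section 4.1 chooses between Wald and Wilson on the observed rate alone, so small denominators can give upper limits above 100%, zero-width intervals and, near 90%, lower limits above Wilson's

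*Combined protocol and SAP*

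**What the plan says.** Section 4.1 builds one two-by-two table per gene locus and takes five rates from it, each with its own fraction, for example "Positive coincidence rate=A/(A+C)×100" and "Positive predictive value (PPV)=A/(A+B)×100". A single 95% interval formula, p ± 1.96 × [p(1-p)/n]^(1/2), then serves all of them: "where p is the positive coincidence rate, negative coincidence rate, positive predictive value, negative predictive value, total coincidence rate, n is the sample size". The only departure is "if p>0.9, use Wilson score method for correction". An observed rate of exactly 0.9 therefore stays with Wald. Section 4.1 gives no truncation to 0-100%, no minimum denominator and no exact method.

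Three other places bear on how much this matters:

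- Section 3.2.1 plans 1052 samples with at least 30% positive, but sets no number of positives per locus. It says that "the rare mutation types shall be counted according to the clinical occurrence" and that "Gene locus below the above standards can no longer be included in clinical data statistics". The standard in that last sentence has no number.
- Section 3.1 sends samples discordant with the marketed products to Sanger sequencing and accepts the Sanger result.
- Section 4.2 has the only numerical threshold for agreement: "When k>0.75, clinical research reagents and comparison methods have good consistency".

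**The concern.** The Wald interval is unreliable when the denominator is small or the rate is near 0 or 1. The plan recognises this by moving to Wilson above 0.9, but it ties the move to the observed rate and not to the amount of data. At a locus with ten comparator positives, one missed positive gives 9/10 and so Wald; at twenty, two missed positives give 18/20 and so Wald.

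The rule also governs PPV, whose denominator A+B is small wherever positives are few. A handful of panel-only positives can bring PPV to 0.9 or below even when both coincidence rates are high.

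At a sparse locus, the interval is what tells the reader how little data support the rate. What is at stake is whether that interval is possible at all and whether its lower limit is credible.

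**Working it through.** **Inputs.** The interval formula, the multiplier 1.96 and the 0.9 switch come from Section 4.1; the total of 1052 comes from Section 3.2.1. The documents state no confidence limit, so there is no figure of the plan's own to reproduce. Counts per locus are not given; every denominator below is an assumption. n is each rate's own denominator.

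**Formulas** (z = 1.96, z² = 3.8416)

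- Wald: p ± z × sqrt(p(1-p)/n)
- Wilson: [p + z²/(2n) ± z × sqrt(p(1-p)/n + z²/(4n²))] / (1 + z²/n)
- Plan: Wald if x/n ≤ 0.9, Wilson if x/n > 0.9

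**Step 1: 9/10 worked through.**

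- Wald: 0.9 ± 1.96 × sqrt(0.09/10) = 0.9 ± 0.186, that is 71.4-108.6%.
- Wilson: [0.9 + 0.192 ± 1.96 × sqrt(0.0090 + 0.0096)] / 1.384 = (1.092 ± 0.267)/1.384, that is 59.6-98.2%.

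**Step 2: other results.**

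| Result | Plan | Wilson | Plan lower limit minus Wilson's |
|---|---|---|---|
| 0/5 | 0-0% | 0-43.4% | 0 |
| 2/3 | 13.3-120.0% | 20.8-93.8% | -7.4 points |
| 9/10 | 71.4-108.6% | 59.6-98.2% | +11.8 |
| 18/20 | 76.9-103.1% | 69.9-97.2% | +7.0 |
| 27/30 | 79.3-100.7% | 74.4-96.5% | +4.9 |
| 45/50 | 81.7-98.3% | 78.6-95.7% | +3.0 |
| 90/100 | 84.1-95.9% | 82.6-94.5% | +1.6 |

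Differences are taken before rounding. The lower limit also drops slightly as the result improves past the switch: 76.9% at 18/20 but 76.4% at 19/20. For a fixed denominator this drop is at most 0.6 points.

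**Step 3: where the upper limit passes 100%.** At p = 0.9 this needs 1.96 × 0.3/sqrt(n) > 0.1, so n < 34.6. An observed 0.9 requires n to be a multiple of 10, so 30 is the last such case. A search over every result for n = 1 to 1052 finds at least one upper limit above 100% at each n from 2 to 30 and none above. The chance of such a limit at true agreement 0.90 / 0.95 is 58% / 39% at n=10, 47.5% / 25% at n=20, 24% / 13% at n=30 and 0% at n=50.

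**Step 4: coverage, by exact binomial sums.**

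- n=10, true rate 0.70. The plan's lower limit exceeds 0.70 at 9/10 (71.4%) and 10/10 (72.2%). The probability is 10 × 0.7^9 × 0.3 + 0.7^10 = 0.121 + 0.028 = 14.9%. Under Wilson only 10/10 does so, 2.8%. Total coverage is 84.0% against 92.4%.
- n=20, true rate 0.75. Coverage is 89.5% against 93.5%; the lower limit is above the truth 9.1% of the time against 2.4%.
- True rates of 0.85 or more. For n = 2 to 139 the plan's coverage is never below Wilson's. For n = 140 to 316 it is lower at some values, by about 2.2 points at most.

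**Step 5: PPV illustration (assumed counts).** Let 19 of 20 positives and 1029 of 1032 negatives agree. Then A=19, C=1, B=3, D=1029, which sum to 1052. Positive coincidence is 95.0% and negative coincidence 99.7%. PPV is 19/22 = 86.4%, with plan limits 72.0-100.7% against Wilson 66.7-95.3%.

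**The case against.** The best reply is that little turns on this. Observed rates above 0.9, including 100% agreement, already get Wilson: 10/10 is reported as 72.2-100%. If true agreement is 0.98, the Wald branch is reached only 6% of the time at n=20 and 2% at n=30. An upper limit of 108.6% is visibly impossible and would mislead nobody. Section 3.2.1 may drop sparse loci, and Sanger resolution under Section 3.1 may shrink the discordant cells and move rates into the Wilson range. All of this limits the scope. None of it reliably prevents the problem: the exclusion standard has no number, and Section 4.1 does not say whether its table uses resolved results. A visibly impossible upper limit also leaves the too-high lower limit in place, where nothing looks wrong.

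A reader might infer that the rule favours the panel whenever the denominator is small. The documents do not support that. At the smallest denominators Wald's lower limit can be the less favourable one (2/3: 13.3% against 20.8%). At true rates of 0.85 or more with small denominators, the plan covers at least as often as Wilson.

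The remedy is also a trade. At n=10 and true rate 0.9825, Wilson's upper limit at 9/10 is 98.21%, just below the truth, so only 10/10 covers: 0.9825^10 = 83.8%. The plan's coverage there is practically 100%. That objection stands and belongs in the cost.

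**Conclusion.** The concern holds, as a minor point about reported precision. Applied as written, Section 4.1 can produce limits above 100% at denominators of 2 to 30, zero width at 0/n, and lower limits several points above Wilson's when the observed rate is near 0.9 and results are few. Genuine under-coverage is mainly at lower true rates with few results. For rates on large denominators, such as total coincidence on about 1052 samples, the effect is negligible (946/1052: lower limit 0.1 points above Wilson's).

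This rests on two assumptions: that some loci have few positives, which per-locus tables with no minimum count make plausible but do not establish, and that n is each rate's own denominator.

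Two stronger readings should be set aside. A reader might take the sample size in the formula to be the 1052 total, which at p = 0.9 would give 88.2-91.8% even with ten positives. The explicit fractions above the formula, and the separate N for the total in Section 4.2, point the other way; the phrase only needs tightening. A reader might also infer that the interval could change whether the panel passes. No confidence limit is an acceptance criterion, and the point estimates and kappa are unaffected.

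**What to change.** In Section 4.1, use the Wilson score interval for all five rates at every value of p, and delete the Wald formula and the 0.9 switch. In the same sentence, state n for each rate: A+C for positive coincidence, B+D for negative coincidence, A+B for PPV, C+D for NPV and A+B+C+D for total coincidence.

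This is one sentence, uses a method the plan already names, and needs no new data. It removes the impossible limits, the zero width and the step at 0.9.

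The cost has two parts. Some lower limits at rare loci become less favourable. At high true agreement with few results, Wilson's coverage can fall clearly below 95%: 92.5% at n=20, true rate 0.95; 91.4% at n=10, 0.95; 83.8% at n=10, 0.9825. The plan has 99.7% or more in each case. These misses are upper limits below the truth, so they do not flatter the panel.

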#### 4.2 Kappa test

The Kappa test method was used to analyze the equivalence of clinical research reagents and comparison methods. Using statistical software, Kappa test was performed on the detection results of clinical research reagents and gold standard, and the k value was calculated. When k>0.75, clinical research reagents and comparison methods have good consistency.

$$Kappa = \frac{P_a - P_c}{1 - P_c}$$
, Where  $P_{a=} = \frac{A + D}{N}$ ,  $P_C = \frac{(A + B)(A + C)}{N} + \frac{(B + D)(C + D)}{N}$ 

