Wherein, in the treatment of non-small cell lung cancer, the main molecular targeted therapy is epidermal growth factor receptor (EGFR). The efficacy of molecularly targeted drugs is significantly different between different lung cancer patients of the same tissue type and different lung cancer pathological tissue types. The EGFR mutation rate in Asian patients with advanced lung adenocarcinoma is as high as 50%, and there are many EGFR tyrosine kinase inhibitor (TKI) is listed in China and used for clinical treatment. In addition to EGFR, anaplastic lymphoma kinase (ALK) fusion gene and ROS1 fusion gene are also divided into subgroups of NSCLC molecules with specific clinical and pathological characteristics, thereby providing new molecular targets for the treatment of lung cancer. In addition, biomarkers related to lung cancer include HER2, KRAS, BRAF V600E gene mutations, and MET exon 14 skipping mutations. At present, the molecular classification of lung cancer plays an important role in guiding clinical treatment plans, drug selection, and establishing an individualized treatment model for molecular classification. Patients with specific genotypes can only benefit from the corresponding targeted drugs. Therefore, effective and accurate detection of tumor gene status and accurate molecular

subtype differentiation of NSCLC patient populations have become an important basis for patient treatment, prognosis evaluation, and efficacy monitoring.

At present, the routine detection methods for clinical gene detection are fluorescent quantitative PCR, nucleic acid sequence determination, FISH and so on. However, to carry out the above-mentioned gene detection at the same time requires the combination of multiple technology platforms and multiple methods. The large sample size requirements, the complex operation process, and the long detection cycle pose very high challenges to personnel, technology, equipment, etc., which is a serious departure from the clinical goal of quickly and accurately obtaining patient clinical medication information.

The Genetron Lung Cancer Panel is developed by Genetron Health (Beijing) Co., Ltd.. It is used to detect EGFR, KRAS, BRAF, HER2, PIK3CA, ALK, ROS1, MET gene mutations or fusions in non-small cell lung cancer patients. The Genetron Lung Cancer Panel is prepared in a clean production workshop that meets the requirements of the "In Vitro Diagnostic Reagent Production Implementation Rules", and has passed the self-test.

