#### 3.3.2 Comparison Method

The specific sites and corresponding kits are shown in the following table

Table 1. Selection of comparison methods for each gene

Gene	Comparison method		
EGFR	cobas EGFR Mutation Test V2		
ALK	Vysis ALK Break Apart FISH Probe Kit		
ROS1	Vysis 6q22 ROS1 Break Apart FISH Probe		
ROS1*	ROS1 gene fusion detection kit (fluorescence PCR method)		
KRAS	KRAS gene mutation detection kit (fluorescence PCR method)		

PIK3CA	PIK3CA gene mutation detection kit (fluorescence PCR method)
BRAF	BRAF gene mutation detection kit (fluorescence PCR method)
MET	/
HER2	/

\* On the basis of choosing the Vysis 6q22 ROS1 Break Apart FISH Probe kit as a comparison method for the ROS1 gene, add no less than 200 samples for ROS1 gene fusion detection kit (fluorescent PCR method) to perform the comparative study of companion diagnostic reagents.

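### No stated result supports or refutes the companion-diagnostic accuracy purpose: kappa above 0.75 has no interval, no coincidence rate has a minimum, and the interval rule can exceed 100%

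*Combined protocol and SAP*

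**What the plan says.** Section 2 makes accuracy for named companion-diagnostic markers part of the main purpose: EGFR exon 19 deletion, L858R and T790M, and ALK and ROS1 fusion.

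Section 4.2 gives kappa the central role: "The Kappa test method was used to analyze the equivalence of clinical research reagents and comparison methods". Its threshold is "When k>0.75, clinical research reagents and comparison methods have good consistency". It asks for no confidence interval on kappa.

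Section 4.1 builds one two-by-two table per locus. From it come the positive and negative coincidence rates, the predictive values, and the "total coincidence rate and 95% confidence interval of the assessment reagent and the comparison method". No rate or limit has a minimum. The interval is the rate plus or minus 1.96 standard errors, with one exception: "if p>0.9, use Wilson score method for correction".

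Section 3.2.1 sets a total of 1052 samples with at least 30% positive overall. For rare types it says "the rare mutation types shall be counted according to the clinical occurrence, which should be statistically significant", and then "Gene locus below the above standards can no longer be included in clinical data statistics". It gives no count per locus. For the second ROS1 comparison, Section 3.3.2 says to "add no less than 200 samples for ROS1 gene fusion detection kit".

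**The concern.** A companion diagnostic is judged mainly on whether it finds the patients who carry the marker. Kappa combines missed positives and false alarms in one number. When a locus has few positives among many negatives, the point estimate can exceed 0.75 while a large share of positives is missed. The rate that would show this, positive agreement, is reported but has no value it must reach.

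A sparse locus could therefore be described as consistent beside a positive agreement whose 95% lower limit is under one half, with no rule on which figure governs. What is at stake is the later accuracy claim. Care within this study is not affected, because Section 6 says results do not guide treatment.

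**Working it through.** The plan has no power or sample-size calculation, so there is no figure of its own to reproduce.

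**Inputs.** The threshold 0.75 is from Section 4.2. N = 1052 is from Section 3.2.1, taken as the number evaluable per locus. N = 200 is the minimum for the ROS1 PCR comparison in Section 3.3.2. The 20 to 50 comparator positives are an assumption, because the documents give no counts per locus. The cells follow Section 4.1: A both positive, B panel-only positive, C missed by the panel, D both negative.

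**Kappa.** Kappa = (Pa − Pc)/(1 − Pc), with Pa = (A + D)/N and Pc = [(A+B)(A+C) + (B+D)(C+D)]/N². Section 4.2 prints N where the standard form has N². That may be a fault of text extraction, and the standard form is used here.

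- 13 of 20 found, B = 0, D = 1032: Pa = 1045/1052 = 0.99335; Pc = (13×20 + 1032×1039)/1052² = 0.96910; kappa = 0.785. With 12 of 20, kappa is 0.746.
- 31 of 50 found, B = 0, D = 1002: Pa = 1033/1052 = 0.98194; Pc = (31×50 + 1002×1021)/1052² = 0.92580; kappa = 0.757. With 30 of 50, kappa is 0.741.

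**Worst tables with kappa above 0.75, over all 31 counts from 20 to 50 positives.** The Wilson 95% limits are [p + z²/2n ± z√(p(1−p)/n + z²/4n²)]/(1 + z²/n), with z = 1.96 and n = A + C for positive agreement.

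| N | Panel-only positives | Share missed | Counts with Wilson lower limit below 50% |
|---|---|---|---|
| 1052 | 0 | 35.0-39.3% | 31 of 31 |
| 1052 | 1 | 33-38% | 30 of 31 |
| 1052 | 5 | 20-32% | 0 of 31 |
| 200 | 0 | 32-36% | 18 of 31 |
| 200 | 1 | 30-33% | 10 of 31 |

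The maximum of 39.3% is at 17/28 (kappa 0.7505). The Wilson lower limits are 43% at 13/20 and 48% at 31/50.

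**How often a weak assay exceeds the threshold.** Exact binomial calculation, N = 1052, true positive agreement 70%:

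| Comparator positives | Negative agreement 99.9% | Negative agreement 99.5% |
|---|---|---|
| 20 | 72% | 32% |
| 50 | 87% | 65% |

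**Interval rule in 4.1.** At 18/20 the rate is exactly 0.9, so the uncorrected formula applies: 0.90 ± 1.96×√(0.9×0.1/20) = 0.90 ± 0.13, or 77-103%. Wilson gives 70-97%. At 17/20 the formula gives 0.85 ± 0.16, or 69-101%, where Wilson gives 64-95%.

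**The case against.** Five points can be made for the plan.

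- **The threshold is a label.** Section 4.2 attaches only a description to kappa above 0.75, with no pass or fail consequence. A reader might infer that kappa is a lax acceptance gate, but the documents do not say so. This stands. It leaves the plan with no success rule at all, and that is the point made here.
- **The illustration is extreme.** With 20 or 50 positives among 1052, the chance of no panel-only positives is about 36-37% at negative agreement 99.9% (0.999 to the power 1032 or 1002) and under 1% at 99.5%. This stands. A reader might infer that the panel is expected to miss over a third of positives; nothing in the documents supports that.
- **Sparsity is assumed.** Section 3.2.1 plans at least 30% positives, and Section 3.2.2.1 item (2) collects some samples with earlier molecular results, which could enrich certain loci. Section 1 puts the EGFR mutation rate as high as 50% in Asian advanced adenocarcinoma, so exon 19 deletion and L858R are unlikely to be sparse. This narrows the concern to loci such as T790M, ALK and ROS1, but gives no count for them.
- **The rates will be visible, and discordant samples go to Sanger review.** Both are true, and they limit concealment. No minimum exists before or after review, and the arithmetic applies to whichever table is used.
- **Sparse loci are dropped under Section 3.2.1.** The standard for dropping them has no count, so it does not close the gap.

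**Conclusion.** The concern holds as a gap in the plan. Equivalence is judged by a kappa point estimate, no coincidence rate has a minimum, and so no stated result supports or refutes the Section 2 accuracy purpose. The interval rule is a separate fault and is wrong as written, because it can give limits above 100%. It does not drive the kappa result: at 13/20 the two lower limits are 44.1% and 43.3%.

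The 35-39% is a worst-case figure. It rests on 1052 evaluable samples at the locus, 20 to 50 comparator positives, no panel-only positives and the standard kappa formula. A lower limit below 50% should not be read as general. It holds at nearly every count at N = 1052 with none or one panel-only positive, at none with five, and at N = 200 at only 18 of 31 counts with none and 10 of 31 with one. The change should be made before unblinding, but the study can run as designed.

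**What to change.** **Section 4.1.** State:

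> Wilson 95% limits are used at every value of p, with n = A + C for the positive and n = B + D for the negative coincidence rate. For each companion-diagnostic locus in Section 2, the conclusion rests on these two rates, each judged against a minimum lower limit fixed by the sponsor before unblinding. All other loci, and any locus that does not reach its minimum, are reported descriptively with counts and Wilson limits.

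**Section 4.2.** Report each kappa with a 95% interval, treat 0.75 as a supporting description at every locus, and check the printed denominator of Pc. A kappa lower limit above 0.75 is not a substitute. At N = 1052 with no panel-only positives it still admits 16/20 and 37/50, whose positive-agreement lower limits are 58% and 60%. With one panel-only positive both fall short (0.743 and 0.749), but 17/20 and 38/50 still clear it.

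**Section 3.2.1.** Show sparse loci descriptively instead of dropping them.

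**Cost.** This needs wording, one interval per kappa, one sponsor decision, and approval by the team-leader institution under Section 5 item (6). The main downside is that sparse loci may become descriptive. Even with every positive found, the Wilson lower limit is 57% at 5/5, 72% at 10/10, 84% at 20/20 and 93% at 50/50. For an illustrative 70% limit, a true 95% assay passes 60% of the time at 10 positives (all 10 needed, 0.95¹⁰), 49% at 14 (all 14 needed, 0.95¹⁴), 74% at 20 (19 needed) and 98% at 30 (26 needed). A true 70% assay passes about 4% of the time or less at the counts checked. The 70% is not a recommendation; the minimum is for the sponsor to set.

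### As it reads in the supplied text, the kappa formula in section 4.2 divides chance agreement by N instead of N², so followed literally it gives kappa of at least 1 for every non-degenerate table

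*Combined protocol and SAP*

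**What the plan says.** Section 4.1 sets up a two-by-two table for each gene locus (Table 2), with cells A, B, C and D. One of its measures is "Total coincidence rate=(A+D)/(A+B+C+D)×100"%. It adds: "Using statistical software, Kappa test is used to determine whether the two detection methods are statistically significant".

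Section 4.2 gives kappa in its usual general form, "Kappa = \frac{P_a - P_c}{1 - P_c"}, takes Pa as (A+D)/N, and defines chance agreement as "P_C = \frac{(A + B)(A + C)}{N} + \frac{(B + D)(C + D)}{N"}. (The quoted formulas are in the notation of the machine-read text and stop just before the closing brace.) On computation it says: "Using statistical software, Kappa test was performed on the detection results of clinical research reagents and gold standard, and the k value was calculated". On interpretation: "When k>0.75, clinical research reagents and comparison methods have good consistency".

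No other section restates or corrects the formula, and the documents give no expected or worked kappa value.

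**The concern.** The numerator and denominator of kappa combine Pa, Pc and 1, so Pa and Pc must both be proportions. Pa is one. Pc as printed is not: a product of two margins divided once by N is an expected count. The formula therefore subtracts a count from a proportion.

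Section 2 makes coincidence rate and consistency the main purpose of the study, and k>0.75 is the plan's only numerical agreement threshold. It serves as a label for good consistency; no section attaches a pass/fail consequence to it. If the printed formula were coded or worked by hand, that label could not distinguish good agreement from chance-level agreement. If kappa comes from a standard software routine, the value is right but does not match the formula in the plan.

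**Working it through.** **Inputs.** The definitions of kappa, Pa and Pc and the 0.75 threshold are from section 4.2. The cell layout and the total coincidence rate are from section 4.1. Two sample sizes are used for illustration: 200, the minimum for the ROS1 PCR comparison (section 3.3.2: "add no less than 200 samples for ROS1 gene fusion detection kit"), and 1052, the total in section 3.2.1. All cell counts below are assumed, because the documents give none. There is no stated kappa in the plan to reproduce.

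**Step 1: what N is.** Pa = (A+D)/N is the total coincidence rate of section 4.1 written as a proportion, so N = A+B+C+D.

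**Step 2: size of the error in Pc.** Let S = (A+B)(A+C) + (B+D)(C+D). Chance agreement is Pe = S/N². The printed Pc is S/N = N × Pe.

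**Step 3: consequence for kappa.** If all four margins are non-zero, S is at least 2(N−1), so printed Pc is at least 2(N−1)/N, which exceeds 1 for N ≥ 3. Then

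printed kappa = (Pa−Pc)/(1−Pc) = (Pc−Pa)/(Pc−1) = 1 + (1−Pa)/(Pc−1).

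Since 1−Pa ≥ 0 and Pc−1 > 0, this is never below 1. For fixed margins Pc is fixed, so the value rises as Pa falls.

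**Step 4: one table in full.** Take A/B/C/D = 9/1/1/189, N = 200.
- S = 10×10 + 190×190 = 36,200.
- Pa = 198/200 = 0.99.
- Correct: Pe = 36,200/40,000 = 0.905; kappa = (0.99−0.905)/(1−0.905) = 0.085/0.095 = 0.895.
- Printed: Pc = 36,200/200 = 181; kappa = (0.99−181)/(1−181) = 180.01/180 = 1.00006.

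**Step 5: a range of tables.**

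| A/B/C/D | N | Pa | Printed Pc | Correct kappa | Printed kappa |
|---|---|---|---|---|---|
| 9/1/1/189 | 200 | 0.990 | 181.0 | 0.895 | 1.00006 |
| 7/3/3/187 | 200 | 0.970 | 181.0 | 0.684 | 1.00017 |
| 4/6/6/184 | 200 | 0.940 | 181.0 | 0.368 | 1.00033 |
| 0/10/10/180 | 200 | 0.900 | 181.0 | −0.053 | 1.00056 |
| 10/11/11/1020 | 1052 | 0.979 | 1010.84 | 0.466 | 1.00002 |
| 306/10/10/726 | 1052 | 0.981 | 609.84 | 0.955 | 1.00003 |
| 250/66/66/670 | 1052 | 0.875 | 609.84 | 0.702 | 1.00021 |
| 158/368/158/368 | 1052 | 0.500 | 526.0 | 0.000 | 1.00095 |

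The first four rows share the same margins and show the printed value rising as agreement falls. The fifth row has about 2% positives. The sixth and seventh have about 30% positives (316/1052). The last is agreement exactly at chance.

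**Step 6: which form software uses.** The kappa routine in the statsmodels package returns 0.8947 for 9/1/1/189, 0.3684 for 4/6/6/184 and 0.4655 for 10/11/11/1020. These match the N² form.

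**Step 7: generality.** Over all 1,373,701 possible tables with N = 200, printed kappa is at least 1 in 1,373,695. The six exceptions have 199 or 200 samples in a single discordant cell: two give 0, and four are undefined because Pc = 1. This shows only that the bound is general; it says nothing about which results are likely.

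**The case against.** Four points can be made for the plan.

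- **The text may be damaged.** The formula was read from PDF by a program, and the definition of Pa beside it is visibly garbled. If the source page set the two fractions over a further N, flattening them would produce exactly this text. This stands as a caveat. Against it, both denominators read plain N, and the exponent in the confidence-interval formula of section 4.1 survived.
- **The planned route is software.** Sections 4.1 and 4.2 both say so, and a standard routine does not use the printed line. This also stands: the reported kappas would probably be right. What remains is a plan whose only kappa formula does not give the value that software reports.
- **The error would show itself.** Values slightly above 1 are impossible for kappa, and someone who knows the statistic can recompute it from the table. This makes a wrong published value less likely, but it does not correct the formula.
- **The examples with few positives exaggerate the contrast.** Section 3.2.1 plans at least 30% positive samples, though whether overall or per locus is unclear. At 30% with good agreement (306/10/10/726), correct and printed kappa both exceed 0.75. At 30% with weaker agreement (250/66/66/670), correct kappa is 0.702 and misses the threshold while the printed value passes. The same section also expects rare mutation types, so low-prevalence tables are relevant.

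These points limit the severity. None of them makes the formula correct as supplied.

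**Conclusion.** The concern holds. As supplied, the section 4.2 formula overstates chance agreement by a factor of N. Taken literally, it puts kappa at or above 1 for every table with non-zero margins and N ≥ 3, so the 0.75 threshold would be met even at chance-level agreement. The algebra needs no assumption about the data; only the illustrative sizes rest on assumed counts.

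This should be fixed, but it is not evidence that reported results would be wrong: the stated software route would probably give correct kappas, no pass/fail decision hangs on the threshold, and the section 4.1 estimates do not use the formula. Confidence is medium, because a loss in reading the equation from PDF cannot be excluded.

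**What to change.** Check the source page for a lost exponent or a lost outer division by N. If the formula is as shown, replace it with

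Pc = [(A+B)(A+C) + (B+D)(C+D)] / N², where N = A+B+C+D for each locus table.

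The cost is one corrected line, plus the approval by the team leader institution that section 5(6) requires for any change to the plan. Samples, testing, the section 4.1 estimates and any kappa from a standard software routine stay as they are.
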